### 19.1. DESCRIPTIVE STATISTICS

The plasma concentrations of encorafenib, binimetinib and the active metabolite of binimetinib (AR00426032) and the serum concentrations of Cetuximab will be tabulated with their related descriptive statistics.

Individual concentrations tables will be presented by drug-related analyte (i.e encorafenib, binimetinib, AR00426032 and cetuximab), by dose (if applicable) and by nominal time points, with

descriptive statistics as number of available data (N), arithmetic mean, StD, CV, geometric mean, geometric CV, median, [min – max] according to the following rules.

Values reported as ‘NS’ (no sample) will be set to ‘missing’.

Encorafenib, binimetinib and AR00426032 concentrations will be flagged and excluded from the descriptive statistics if a vomiting episode occurs within the first 4 hours post-dosing of during the day of the last dose prior to collection of PK samples.

Concentrations will be flagged and excluded from the descriptive statistics if the actual sampling time is outside the nominal sampling time predefined window (i.e T2h  $\pm$ 10 min and T6h  $\pm$  30 min).

For calculated statistics, by time point, if more than (or equal) half of values are not BLQ, statistics will be calculated considering BLQ values as missing data, but Min value will take into account BLQ (i.e Min = BLQ). If more than half of values are BLQ: arithmetic and geometric means, StD, CV geometric CV, median will not be calculated and only Min (BLQ) and Max values will be presented. By time point, if all the concentration values are BLQ, the corresponding statistics will be indicated as not applicable (NA).

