Table 21: Summary of Clinical Laboratory Tests_ Study extension period	135
Table 22: Modified NCI CTCAE, Version 4.03 Grading for Hypertension	138
Table 23: Modified NCI CTCAE, Version 4.03 Grading for Hypotension	138
Table 24: Eastern Cooperative Oncology Group (ECOG) Performance Status Scale	142
Table 25: Biomarker samples_ Main study period	145
Table 26: Biomarker samples_ Study extension period	146

Figure

Figure 1: Graphic representation for pharmacokinetic sampling plan*	129
---	-----

SYNOPSIS

Name of Sponsor:	Pierre Fabre Médicament represented by the Institut de Recherche Pierre Fabre (IRPF)
Name of Finished Product:	Encorafenib, Binimetinib, Cetuximab
Title of the Study:	Phase II, open-label, single arm, multicenter study of encorafenib, binimetinib plus cetuximab in subjects with previously untreated BRAF ^{V600E} -mutant Metastatic Colorectal Cancer.
Study Coordinating Investigator:	PII [redacted] PII [redacted]
Study Centre(s):	Approximately 70 centers in Europe, North America and Japan

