1.2.3. CETUXIMAB

Chemical and pharmaceutical characteristics

Cetuximab is a recombinant, human/mouse chimeric monoclonal antibody that binds specifically to the extracellular domain of human EGFR on both normal and tumor cells, and inhibits receptor activation by competing with the epidermal growth factor and other ligands. In vitro and in vivo assays have shown that binding of cetuximab to the EGFR blocks its dimerization and phosphorylation and its consequent activation, resulting in an inhibition of cell growth, induction of apoptosis, and decreased matrix metalloproteinase and vascular endothelial factor production. Cetuximab exhibits clinical activity as a monotherapy or in combination with chemotherapy and/or radiation in head and neck cancer and mCRC (Cunningham D et al, 2004; Baselga J et al, 2005; Bonner JA, et al 2006).

Cetuximab is approved in about 100 countries for the treatment of patients with epidermal growth factor receptor (EGFR)-expressing, RAS wild-type metastatic colorectal cancer

- in combination with irinotecan-based chemotherapy,
- in first-line in combination with FOLFOX,
- as a single agent in patients who have failed oxaliplatin- and irinotecan-based therapy and who are intolerant to irinotecan (see the locally applicable cetuximab label).

Nonclinical data

Following the recommended dose regimen (400 mg/m² initial dose; 250 mg/m² weekly dose), concentrations of cetuximab reach steady-state levels by the third weekly infusion. Cetuximab has a long elimination half-life with values ranging from 70 to 100 hours at the target dose. Although the US label for Erbitux® indicates that US-licensed cetuximab (Erbitux®) provides approximately 22% greater exposure relative to cetuximab which is approved in the European Union (EU), the dosing and administration guidelines are consistent between the regions.

Clinical data

In subjects with mCRC whose disease had progressed during or within 3 months after treatment with an irinotecan-based regimen, treatment with single-agent cetuximab resulted in an objective response rate of 11% and a median time to progression of 1.5 months (**Cunningham D et al, 2004**).

In subjects with EGFR-expressing mCRC treated with cetuximab in combination with irinotecan in the second-line setting, the median PFS was 4.0 months (95% confidence interval [CI], 3.24.1 months) and OS was 10.7 months (95% CI, 9.6 -11.3 months) (**Sobrero AF et al, 2008**).

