6. STUDY TREATMENT(S)

In Europe (EU), the Investigational Medicinal Product Management Service of the *Institut de Recherche Pierre Fabre (IRPF)* will supply the investigational centers with labeled and packaged encorafenib, binimetinib and cetuximab units necessary for the conduct of the trial.

In the United States (US), labeled and packaged binimetinib and encorafenib will be supplied to investigational centers by Array BioPharma. Cetuximab supply within the US will be supplied either locally or by Array BioPharma. Array BioPharma will employ a licensed company specializing in packaging, labeling, and distribution of investigational medicinal products.

In Japan (JAP), labeled and packaged binimetinib, encorafenib and cetuximab will be supplied to investigational centers by Array BioPharma via a licensed company specializing in packaging, labeling, and distribution of investigational medicinal products via a warehouse facility located in Japan.

6.1. SOURCE, PRESENTATION AND COMPOSITION OF INVESTIGATIONAL PRODUCT(S) AND ASSOCIATED PRODUCT(S)

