6.1.3. Cetuximab solution for infusion

Cetuximab is available under different formulations:

- 1 formulation for Europe and Japan
- 1 formulation for US
- **Europe and Japan formulation: ERBITUX® 5 mg/mL solution for infusion**

Cetuximab solution for infusion will be supplied in labelled packages : single-use vial of 500 mg cetuximab (5 mg/mL solution) – vial of 100 mL

Cetuximab is a colorless solution administered intravenously.

Cetuximab is a chimeric monoclonal IgG1 antibody produced in a mammalian cell line (Sp2/0) by recombinant DNA technology.

Composition:

- **Active ingredient:** Cetuximab 5 mg/mL
- **List of excipients:** Sodium chloride, Glycine, Polysorbate 80, Citric acid monohydrate, Sodium hydroxide, Water for injection.

Cetuximab does not contain any antimicrobial preservative or bacteriostatic agents. From a microbiological point of view, the product should be used immediately after opening. If not used immediately, in-use storage times and conditions prior to use are the responsibility of the user and would normally not be longer than 24 hours at 2 to 8°C, unless opening has taken place in controlled and validated aseptic conditions.

- **US formulation**

Erbix®(cetuximab) in the US is commercially available and is supplied at a concentration of 2 mg/mL as a 100 mg/50 mL, single-use vial or as a 200 mg/100 mL, single-use vial as a sterile injectable liquid containing no preservatives.

Composition:

Cetuximab is formulated in a solution with no preservatives, which contains:

- **Active ingredient:** Cetuximab 2 mg/mL
- **List of excipients:** sodium chloride, sodium phosphate dibasic heptahydrate, sodium phosphate monobasic monohydrate, and Water for Injection

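### SAP 19.1 does not separate the two cetuximab products, so if US subjects are in the PK set the serum summary mixes them and mainly misstates the US product

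*SAP*

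**What the plan says.** Describing the pharmacokinetics of cetuximab is a secondary objective, and its serum concentration is a secondary endpoint (Protocol 2.2 and 2.5; SAP 6.2 and 6.3.2). The committed analysis is a descriptive table. SAP 19.1 builds it "by drug-related analyte (i.e encorafenib, binimetinib, AR00426032 and cetuximab), by dose (if applicable) and by nominal time points", and SAP 19 applies it to a single PK set covering all regions. Protocol 13.14 adds no further stratum. Population PK is optional and is left to a separate modelling plan and report (Protocol 13.14; SAP 19.2).

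The protocol describes two cetuximab products. Section 6.1.3 lists "1 formulation for Europe and Japan" (5 mg/mL) and "1 formulation for US" (2 mg/mL), section 6 provides for supply to US sites, and the synopsis plans "Approximately 70 centers in Europe, North America and Japan". On the difference between products, Protocol 1.2.3 cites the US label: "US-licensed cetuximab (Erbitux®) provides approximately 22% greater exposure relative to cetuximab which is approved in the European Union (EU". It adds that "the dosing and administration guidelines are consistent between the regions".

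**The concern.** The protocol itself reports an exposure difference between two products that it gives at the same dose, yet the one committed summary of cetuximab concentrations has no product stratum. A mean taken over both products depends on how many US subjects happen to be in the PK set. A reader who sets it beside data on the US product alone would be comparing unlike things. What is at stake is how well one descriptive secondary objective can be read. No efficacy or safety decision rests on it.

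**Working it through.** **Inputs**

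- Exposure ratio, US to Europe/Japan: 1.22 (Protocol 1.2.3, from the US label). The documents give no data from which to reproduce it and do not say whether it refers to AUC, peak or trough.
- US share of the PK set, w: not stated. Assumed 10, 20, 30 and 50%.
- Coefficient of variation (CV) within a product: not stated. Assumed 20 to 40%.
- Size of the PK set: taken as 90, the planned number of centrally confirmed subjects (Protocol 13.3), as a stand-in.

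**Step 1: can the planned strata separate the products?**

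- *Dose.* Cetuximab is sampled on Cycle 1 Day 1 and Cycle 2 Day 1 (Protocol 8.2.1; SAP 19), when the planned doses are 400 and 250 mg/m² in every region. The last subject started on 27 Dec 2019, so the last scheduled Cycle 2 Day 1 is 28 days later, 24 Jan 2020. That precedes the 26 Mar 2020 measure on two-weekly infusions. Dose therefore does not track product.
- *Japan subgroup.* The list of Japan analyses in SAP 20 does not name PK. Japan also shares the European formulation, so that split would not isolate the US product.
- *Modelling.* It is optional, and neither document names a product covariate.

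None of the three separates the products.

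**Step 2: shift of the pooled mean**

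With the single-product value as the base:

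- geometric mean against Europe/Japan: 1.22^w − 1; against US: 1.22^(w−1) − 1
- arithmetic mean against Europe/Japan: 0.22w; against US: (1 + 0.22w)/1.22 − 1

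For w = 0.2: 1.22^0.2 = 1.041, and 1.041/1.22 = 0.853.

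| US share | Geometric, vs Europe/Japan | Geometric, vs US | Arithmetic, vs Europe/Japan | Arithmetic, vs US |
|---|---|---|---|---|
| 10% | +2.0% | −16.4% | +2.2% | −16.2% |
| 20% | +4.1% | −14.7% | +4.4% | −14.4% |
| 30% | +6.1% | −13.0% | +6.6% | −12.6% |
| 50% | +10.5% | −9.5% | +11.0% | −9.0% |

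**Step 3: spread**

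Mixing adds w(1−w)·(ln 1.22)² to the log-variance. This is largest at w = 0.5: 0.25 × 0.199² = 0.0099. For a within-product CV of 30% the log-variance is ln(1.09) = 0.0862. The total is 0.0961, and the pooled CV is √(e^0.0961 − 1) = 31.8%.

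**Step 4: sampling error for scale**

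With s = √ln(1 + CV²), the 95% half-width of a geometric mean on 90 subjects is exp(1.96·s/√90) − 1. That gives 4.2, 6.3 and 8.3% for CVs of 20, 30 and 40%. At US shares of 10 to 20% the shift from the Europe/Japan value (2.0 to 4.1%) is inside this band. The shift from the US value (14.7 to 16.4%) is well outside it.

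**Step 5: size of a US cell**

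A 10% share of 90 is 9 subjects. With a CV of 30%, s = 0.294 and the half-width is exp(1.96 × 0.294/3) − 1, about 21%, which is as large as the product difference itself.

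**The case against.** The case for leaving the table alone has substance.

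- *The US share is unknown.* Sites in North America and US supply are planned, but neither document says how many US subjects entered, or that any did. With none, the point is moot.
- *The 22% may not carry over.* It is a label statement about exposure in general. The trial takes sparse samples: 2 h and 6 h after the start of infusion in Cycle 1, then pre-infusion and 2 h in Cycle 2. Nothing in the documents shows a 22% difference at those times.
- *The SAP is silent rather than explicit.* It does not state that products are pooled. The list of tables is in an external file (SAP Appendix 5), and that file and the modelling plan were not available for this check.
- *The information is not lost.* Individual listings are planned (SAP 9.2), the subject code carries the country number (Protocol 5.6), and the PK set is to be counted by country (SAP 12).
- *The use is descriptive.* SAP 8 treats everything but the primary test as exploratory.

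All of this stands, and it limits the size and certainty of the point. It does not remove it: a table built as SAP 19.1 specifies would combine the products, and listings are no substitute for a summary by product.

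A reader might also infer that the mixture would hide an interaction with encorafenib or binimetinib, or spoil an exposure-response analysis. The documents do not support that. They plan no interaction test and no comparison with labels or historical data, and they leave exposure-response to a separate plan, to be done only if appropriate.

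**Conclusion.** The point holds as a modest improvement to one secondary descriptive analysis. If US subjects are in the PK set, the pooled cetuximab summary mixes two products for which the protocol itself cites an exposure difference, and none of the planned strata separates them. The error falls mainly on the US product: 9.5 to 16.4% too low on the geometric mean for assumed US shares of 50% down to 10%, if the 22% applies at the sampled times.

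A reader might go further and conclude that the summary describes neither product. That depends on the US share, which is not given. At 10 to 20% the pooled mean is within about 4% of the Europe/Japan value and describes that product well. Nor is the reported variability distorted in any way that matters. The primary test of confirmed response rate is not affected.

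**What to change.** In SAP 19.1, tabulate cetuximab concentrations by product (US versus Europe/Japan), assigned from country or the supply record, with N per product, in addition to dose and nominal time. Keep the pooled table as secondary. If population PK is done, list product as a candidate covariate in the modelling plan. State there that product coincides with region, so that neither a split nor a covariate can say which of the two causes a difference.

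The cost is one extra stratum in one table, using data already held. The SAP analyses PK once, at the end-of-study analysis (SAP 12 and Appendix 5), so no stage 1 or stage 2 output would need rerunning. The downside is that US cells may be small. The split would then show which product each figure belongs to without estimating the difference precisely, which is why N should appear beside every product-specific summary.

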- Change from baseline in the European Organization for Research and Treatment of Cancer (EORTC) Quality of Life Questionnaire for Cancer subjects (QLQ-C30), EuroQol-5D-5L (EQ-5D-5L), and Patient Global Impression of Change (PGIC).
- Resource utilization focused on hospitalizations occurring during the study treatment phase.

- Plasma concentrations of encorafenib, binimetinib and the active metabolite of binimetinib (AR00426032) and serum concentration of cetuximab.

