## 8. INFERENCE PRINCIPLES

Only the test on the primary efficacy endpoint, on which is based the sample size justification, may lead to a causal interpretation. All other statistical results are to be regarded within an exploratory perspective.

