## 19. PHARMACOKINETICS ANALYSIS

Blood samples for encorafenib, binimetinib and the active metabolite of binimetinib (AR00426032) plasma concentration measurements will be performed as follow:

	Cycle 1 Day 1		Cycle 2 Day 1	
Time after encorafenib/ binimetinib dosing on designated dosing days (h)	2	6	0 (Pre-dose)	2
PK sample for encorafenib, binimetinib and AR00426032	x	x	x	x

Abbreviations: h = hours; PK = pharmacokinetic

PK samples will be collected on Cycle 1 Day 1 postdose (encorafenib/binimetinib) at 2 h (± 10 min) and 6 h (± 30 min). PK samples will be collected on Cycle 2 Day 1 predose (just prior to encorafenib/binimetinib dose) and postdose at 2 h (± 10 min). Blood samples for encorafenib/binimetinib PK will be processed to collect plasma.

Blood samples for serum Cetuximab concentration measurements will be performed as follow:

	Cycle 1 Day 1		Cycle 2 Day 1	
Time after the start of cetuximab infusion on designated dosing days (h)	2	6	0 (Pre-infusion)	2
PK sample for cetuximab	x	x	x	x

Abbreviations: h = hours; PK = pharmacokinetic

PK samples will be collected on Cycle 1 Day 1 post-infusion (cetuximab) at 2 h (± 10 min) and 6 h (± 30 min). PK samples will be collected on Cycle 2 Day 1 pre-infusion (just prior to infusion of cetuximab) and post-infusion at 2 h (± 10 min). Blood samples for cetuximab PK will be processed to obtain serum. Time points are based on the start of infusion.

The pharmacokinetic set (cf section 7) will be used to perform the PK analysis.

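### SAP 19.1 drops below-limit PK concentrations as missing, so medians and means are overstated at any time point where such values occur

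*SAP*

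**What the plan says.** SAP 19.1 sets three cases for each time point.

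- **Up to and including half BLQ** (the SAP's condition is "if more than (or equal) half of values are not BLQ"): the BLQ results are left out of everything except the minimum, in the words "statistics will be calculated considering BLQ values as missing data, but Min value will take into account BLQ".
- **More than half BLQ**: "If more than half of values are BLQ: arithmetic and geometric means, StD, CV geometric CV, median will not be calculated". Min (shown as BLQ) and Max are then the only entries.
- **All BLQ**: the statistics are marked not applicable.

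The tables are to show "descriptive statistics as number of available data (N), arithmetic mean, StD, CV, geometric mean, geometric CV, median" and the range. The same section sets no-sample results to missing. It also excludes oral-drug concentrations after early vomiting, and any concentration sampled outside its time window.

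The sampling plan in SAP 19 has four samples per analyte. Three are taken 2 h or 6 h after dosing or after the start of infusion. The fourth is a trough; for the oral drugs, "PK samples will be collected on Cycle 2 Day 1 predose (just prior to encorafenib/binimetinib dose) and postdose at 2 h". SAP 6.3.2 lists as a secondary endpoint "Plasma concentrations of encorafenib, binimetinib and the active metabolite of binimetinib (AR00426032) and serum concentration of cetuximab". Protocol 13.14 adds no rule for BLQ values, and neither document plans a sensitivity analysis for these summaries.

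**The concern.** A BLQ sample was taken and assayed, and it is known to lie below every quantified value. Treating it like a sample that was never taken discards that knowledge. The remaining statistics then describe only the upper part of the distribution, while Min in the same row reflects all samples.

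The median does not need this. As long as fewer than half of the values are BLQ, ranking them lowest gives the median of all samples with no imputed value.

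The tables may also hide how far a row is affected. N is the number of available data, but the SAP does not say whether BLQ samples count, and it does not ask for the number or percentage BLQ. The SAP is not uniform either: section 11.2.2 replaces a safety laboratory value reported as below a limit by that limit and does not drop it.

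At stake is the description of drug exposure, a stated secondary objective. These tables are the only PK summary to which this SAP commits, because PK parameters are optional and are left to a separate modelling plan and report.

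**Working it through.** **Direction.** Every BLQ value is lower than every quantified value. Removing any of them therefore raises the arithmetic and geometric means and, apart from ties, the median. This needs no distributional assumption.

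**Size.** The plan has no figure of its own to reproduce: no limit of quantification, BLQ share or expected variability is given. The following are assumptions: log-normal concentrations, BLQ share f, and geometric CV of 100% (equal to the arithmetic CV for a log-normal).

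Let s = √ln(1 + CV²), a = z(f) the standard normal quantile, and λ = φ(a)/(1 − f). Ratios of the reported to the all-sample value are:

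- median: exp(s · z((1 + f)/2))
- geometric mean: exp(s · λ)
- arithmetic mean: Φ(s − a)/(1 − f)

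The reported geometric CV is √(exp(v) − 1), with v = s²(1 + aλ − λ²). The reported CV is √(m₂/m₁² − 1), with m₁ = exp(s²/2)Φ(s − a)/(1 − f) and m₂ = exp(2s²)Φ(2s − a)/(1 − f).

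**Worked case, 30% BLQ.** s = √ln 2 = 0.8326; a = −0.5244; φ(a) = 0.3477; λ = 0.3477/0.70 = 0.4967.

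- Median: z(0.65) = 0.3853; exp(0.8326 × 0.3853) = 1.38
- Geometric mean: exp(0.8326 × 0.4967) = 1.51
- Mean: Φ(1.3570)/0.70 = 0.9126/0.70 = 1.30
- Geometric CV: v = 0.6931 × (1 − 0.2605 − 0.2467) = 0.3416; √(exp(0.3416) − 1) = 64%

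**Range over the BLQ share, true CV 100%.**

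| BLQ share | Median | Geometric mean | Mean | Reported CV | Reported geometric CV |
|---|---|---|---|---|---|
| 0% | 0% | 0% | 0% | 100% | 100% |
| 2% | +2% | +4% | +2% | 98% | 93% |
| 5% | +5% | +10% | +5% | 96% | 87% |
| 10% | +11% | +18% | +9% | 93% | 80% |
| 30% | +38% | +51% | +30% | 81% | 64% |
| 50% | +75% | +94% | +60% | 71% | 54% |

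With CV 50%, the median, geometric mean and mean rise by 3%, 5% and 4% at 5% BLQ, 6%, 10% and 7% at 10%, and 38%, 46% and 36% at 50%.

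**StD.** Its ratio is the reported CV over the true CV, times the mean ratio. At CV 100% and 30% BLQ this is 0.811 × 1.304 = 1.06. It rises by 3%, 6% and 9% at 20%, 30% and 40% BLQ. At CV 60% it falls by about 3 to 4% over the same shares.

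**Check by simulation** (90 subjects, CV 100%): median, geometric mean and mean ratios were 1.11, 1.18 and 1.09 at 10% BLQ, and 1.31, 1.43 and 1.25 at 25%. The formulas give 1.11, 1.18 and 1.09, and 1.30, 1.42 and 1.25.

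**The edge at one half.** At exactly 50% BLQ the reported median is the (1 + 0.50)/2 = 75th percentile of all samples. Just above 50%, no median is reported.

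**The case against.** The strongest reply is that nothing in the documents shows that BLQ values will occur. With none there is no bias, and with 2% the overstatement is only 2 to 4% even at CV 100%. This stands, and it rules out the tempting reading that exposure in this trial is overstated.

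Nor are all four samples clearly at risk. Three follow shortly after a dose or the start of an infusion. For cetuximab even the trough is an unlikely place for BLQ values. Protocol 1.2.3 gives a half-life of 70 to 100 h, so at a weekly interval of 168 h between 168/100 = 1.68 and 168/70 = 2.4 half-lives have passed. Under simple first-order decay, about 31% to 19% of the level remains. The Cycle 2 Day 1 pre-dose sample for the oral analytes is the most plausible place, and that is itself an assumption.

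Some BLQ troughs may come from subjects whose dosing was interrupted, since Protocol 5.7.1 allows interruptions of up to 28 days before discontinuation. The truncated log-normal would then not fit, and substituting a fixed value such as half the limit would mix off-drug subjects into the mean. This is a fair reason not to insist on substitution. It does not support silent deletion: if off-drug samples are to be left out, that should be a stated exclusion, like those for vomiting and sampling time.

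The SAP also has safeguards. Individual concentrations are tabulated, Min displays BLQ in affected rows, and summaries are suppressed when more than half are BLQ. These show that BLQ values exist. They neither correct the median nor state the share in the summary table.

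Finally, SAP 8 says: "All other statistical results are to be regarded within an exploratory perspective". No decision rule in the plan uses these tables. That limits the weight of the point but does not remove it.

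**Conclusion.** The rule is wrong as written, and its effect is conditional. At any time point with some, but not more than half, BLQ values, the reported mean and geometric mean are too high, and so is the median apart from ties. In the log-normal scenarios the CV and geometric CV are too low. A reader might infer that all measures of spread are understated; the StD can rise or fall, so that does not follow.

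The size cannot be derived from the documents. Under the assumed CV of 100% it runs from nil with no BLQ values to 75% for the median, 94% for the geometric mean and 60% for the mean at the 50% limit. Lower variability gives smaller figures.

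The consequence is limited to descriptive, exploratory PK tables. The primary confirmed response-rate test is unaffected. Nothing can be said about the optional population PK model, whose BLQ handling belongs to a plan not included here.

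**What to change.** Amend one paragraph of SAP 19.1:

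- Compute the median on all assayed samples that remain after the section's stated exclusions, with BLQ values ranked lowest. Report it as BLQ if it falls below the limit.
- Report the number and percentage BLQ for each analyte and time point.
- State whether N counts BLQ samples.
- Label any mean, geometric mean or CV computed without BLQ values as based on quantifiable samples only.

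Whether to go further and use a substituted value or a censored-data estimate for the means is a trade-off that can be left to the sponsor.

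The cost is slightly more table work. Reported medians become lower by an amount that depends on the BLQ share, and do not change where there are no BLQ values.
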